11.2 Definitions

11.2.1 Evaluable For Adverse Events

Any patient who receives at least one dose of the study drug(s) or who experiences

a dose-limiting toxicity is considered evaluable for Adverse Events. In addition, for the dose-escalation portion during Cycle 1, patients must receive all prescribed doses of pevoneditat and at least 85% of the prescribed dose of irinotecan and temozolomide per protocol guidelines and must have the appropriate toxicity monitoring studies performed to be considered evaluable for dose limiting toxicity. Patients who do not have DLT and are not considered evaluable for toxicity will be replaced.

11.2.2 Maximum Tolerated Dose

- The MTD will be the maximum dose at which fewer than one-third of patients experience DLT (See [Section 5.5](#)) during Cycle 1 of therapy.
- In the unlikely event that two DLTs observed out of 6 evaluable patients are different classes of Adverse Effects (e.g. hepatotoxicity and myelosuppression), AND all of the following conditions are met, expansion of the cohort to 12 patients will be considered:
 - One of the DLTs does not appear to be dose-related
 - The Adverse Effects are readily reversible
 - The study chair, DVL statistician, DVL committee chair or vice chair, and IND sponsor all agree that expansion of the cohort is acceptable

If fewer than 1/3 of patients in the expanded cohort experience dose-limiting toxicities, the dose escalation can proceed.

- The DLTs observed in the pharmacokinetic (PK) expansion cohort will be counted towards the total number of DLTs observed at the MTD during the dose escalation portion of the study. If $\geq 1/3$ of the cohort of patients at the MTD (during the dose escalation plus the PK expansion) experience DLT then the MTD will be exceeded.

11.3 **Dose Escalation and Determination of MTD**

The rolling six phase 1 trial design will be used for the conduct of this study.³⁵ Two to six patients can be concurrently enrolled onto a dose level, dependent upon (1) the number of patients enrolled at the current dose level, (2) the number of patients who have experienced DLT at the current dose level, and (3) the number of patients entered but with tolerability data pending at the current dose level. Accrual is suspended when a cohort of six has enrolled or when the study endpoints have been met.

Dose level assignment is based on the number of participants currently enrolled in the cohort, the number of DLTs observed, and the number of participants at risk for developing a DLT (i.e., participants enrolled but who are not yet assessable for toxicity). For example, when three participants are enrolled onto a dose cohort, if toxicity data is available for all three when the fourth participant entered and there are no DLTs, the dose is escalated and the fourth participant is enrolled to the subsequent dose level. If data is not yet available for one or more of the first three participants and no DLT has been observed, or if one DLT has been observed, the new participant is entered at the same dose level. Lastly, if two or more DLTs have been observed, the dose level is de-escalated. This process is repeated for participants five and six. In place of suspending accrual after every three participants, accrual is only suspended when a cohort of six is filled. When participants are inevaluable for toxicity, they are replaced with the next available participant if escalation or de-escalation rules have not been fulfilled at the time the next available participant is enrolled.

onto the study.

The following table provides the decision rules for enrolling a patient at (i) the current dose level (ii) at an escalated dose level, (iii) at a de-escalated dose level, or whether the study is suspended to accrual:

# Pts Enrolled	# Pts with DLT	# Pts without DLT	# Pts with Data Pending	Decision
2	0 or 1	0, 1 or 2	0, 1 or 2	Same dose level
2	2	0	0	De-escalate*
3	0	0, 1 or 2	1, 2 or 3	Same dose level
3	1	0, 1 or 2	0, 1 or 2	Same dose level
3	0	3	0	Escalate**
3	≥ 2	0 or 1	0 or 1	De-escalate*
4	0	0, 1, 2 or 3	1, 2, 3 or 4	Same dose level
4	1	0, 1, 2 or 3	0, 1, 2 or 3	Same dose level
4	0	4	0	Escalate**
4	≥ 2	0, 1 or 2	0, 1 or 2	De-escalate*
5	0	0, 1, 2, 3 or 4	1, 2, 3, 4 or 5	Same dose level
5	1	0, 1, 2, 3 or 4	0, 1, 2, 3 or 4	Same dose level
5	0	5	0	Escalate**
5	≥ 2	0, 1, 2 or 3	0, 1, 2 or 3	De-escalate*
6	0	0, 1, 2, 3, or 4	2, 3, 4, 5 or 6	Suspend
6	1	0, 1, 2, 3 or 4	0, 1, 2, 3 or 4	Suspend
6	0 or 1	5 or 6	0 or 1	Escalate**
6	≥ 2	0, 1, 2, 3 or 4	0, 1, 2, 3 or 4	De-escalate*

* If six patients already entered at next lower dose level, the MTD has been defined.

** If final dose level has been reached, the recommended dose has been reached.

If two or more of a cohort of up to six patients experience DLT at a given dose level, then the MTD has been exceeded and dose escalation will be stopped (see [Section 11.2.2](#) for exception to rule).

In addition to determination of the MTD, a descriptive summary of all toxicities will be reported.

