5.4.2 Part A2: Inter-Patient Escalation

Patients enrolling on Part A2 of the study will enroll one dose level behind the dose level at which patients in Part A1 are enrolling. Part A2 will open to enrollment on Dose Level 1 once Part A1 has escalated to Dose Level 2. Once the MTD is determined in Part A1, patients may enroll onto the Part A1 MTD. If at any time 2 or more evaluable patients at a lagging dose level experience a DLT, Part A2 will close to further accrual.

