Amendment 5 will add dose level 4 (35 mg/m²) to the dose escalation part of this study. This amendment will require a minimum of 2 evaluable patients and a maximum of 15 additional patients. The maximum includes 6 patients at dose level 4, 6 additional patients for PK analysis, and 20% inevaluability. The current enrollment rate is approximately 1 patient per month, and this number is expected to be accrued within 15 months. If dose level 4 is expanded to 12 patients due to DLTs of different classes, then the absolute maximum number of patients enrolled is 23. This would require up to 23 months for accrual.

Part A2 is expected to enroll a maximum of 15 patients including 6 at dose level 3, 6 at dose level 4, and 20% inevaluability.

As of 6/30/19, total of 18 patients have been enrolled in Part A1. No patients have enrolled in Part A2. Therefore, the maximum number of patients required to complete this study overall is expected to be 48, and the absolute maximum is 56.

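### At the final dose level, three DLT-free patients can be enough to declare the recommended dose; require six evaluable patients before that declaration

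*Combined protocol and SAP*

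**What the plan says.** Section 11.3 uses a rolling six design. With three patients enrolled, the rule is that "if toxicity data is available for all three when the fourth participant entered and there are no DLTs, the dose is escalated". The table gives the same decision for four of four and five of five DLT-free patients, and for six patients with at most one DLT. All four rows carry the double-asterisk footnote: "If final dose level has been reached, the recommended dose has been reached". The single-asterisk footnote covers the level below one that was too toxic: "If six patients already entered at next lower dose level, the MTD has been defined".

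The final level is set in 11.1: "Amendment 5 will add dose level 4 (35 mg/m²) to the dose escalation part of this study". The same paragraph mentions six patients at that level only within a ceiling: "The maximum includes 6 patients at dose level 4, 6 additional patients for PK analysis, and 20% inevaluability". Nothing in 11.1 to 11.3 makes six a condition for the declaration.

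Section 11.2.2 sets the standard: "The MTD will be the maximum dose at which fewer than one-third of patients experience DLT". It also provides the later check: "The DLTs observed in the pharmacokinetic (PK) expansion cohort will be counted towards the total number of DLTs observed at the MTD". If one-third or more of the pooled patients have a DLT, the MTD is exceeded. For infants, 5.4.2 says: "Once the MTD is determined in Part A1, patients may enroll onto the Part A1 MTD".

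**The concern.** At a lower level, escalating after three clean patients does not settle the trial's answer, because the design goes on to test the next dose. At Dose Level 4 there is no next dose. The same row ends escalation and supplies the answer to primary aim 1.1.1. Section 2.6 places this level above the adult combination MTD of 20-25 mg/m² and reports that exposure rose more than in proportion to dose.

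Three clean patients say little about a one-third limit. The one-sided 95% upper bound on the DLT rate is 1 − 0.05^(1/3) = 63% after 0/3, against 1 − 0.05^(1/6) = 39% after 0/6. A dose at or above the limit is therefore declared more often than it would be if six were required.

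The wording adds a second problem. The footnote yields a recommended dose, while the pooled check in 11.2.2 and the infant rule in 5.4.2 and 11.1 refer to the MTD. The plan does not say that these are the same thing.

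**Working it through.** **The plan's own figures.** Section 11.1 gives 6 patients at Dose Level 4, 6 PK patients and 20% inevaluability: 12/0.8 = 15, as stated. With expansion to 12, 18/0.8 = 22.5, so 23, as stated. The overall totals also reproduce: 18 + 15 + 15 = 48 and 18 + 23 + 15 = 56. The plan gives no operating characteristics for the table.

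**Inputs.** The decision table and footnotes (11.3); the one-third limit and pooled rule (11.2.2); about one patient per month (11.1); a DLT window of Cycle 1, 28 days (5.6, 5.1). The true DLT rate p is not in the documents, so I take 1/3, 40% and 50%. The discretionary expansion to 12 patients is left out on both sides.

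**Step 1: declaration.** Write q = 1 − p. Assume the first three patients are complete before a fourth enrols. As written, the dose is declared after 0/3, or after 1/3 followed by 0 of the next three:

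P(as written) = q³ + 3pq⁵. With six required: P(X ≤ 1), X ~ Bin(6, p) = q⁶ + 6pq⁵.

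At p = 1/3: 0.2963 + 0.1317 = 0.428, against 0.0878 + 0.2634 = 0.351.

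| True DLT rate | As written | Six required | Difference |
|---|---|---|---|
| 1/3 | 42.8% | 35.1% | 7.7 points |
| 40% | 30.9% | 23.3% | 7.6 points |
| 50% | 17.2% | 10.9% | 6.3 points |

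**Step 2: accrual timing.** Assume Poisson accrual at one per month (30.4 days), with therapy starting at enrolment. The chance that the next patient arrives after the latest one has finished 28 days is h = exp(−28/30.4) = 0.398. A DLT-free cohort then closes at three with probability h = 40%, at four with (1−h)h = 24%, at five with (1−h)²h = 14%, and at six with (1−h)³ = 22%. Acceptance becomes

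hq³ + h(1−h)q⁴ + h(1−h)²q⁵ + (1−h)³q⁶ + pq⁵[3 + (1−h) + (1−h)² + (1−h)³].

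This gives 38.7% at p = 1/3, 26.9% at 40% and 13.8% at 50%. The excess over six required is 3.6, 3.5 and 2.9 points.

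**Step 3: after the PK cohort.** Return to the timing in step 1 and apply the pooled rule. Six PK patients after 0/3 make nine, acceptable with at most 2 DLTs. Six PK patients after 1/6 make twelve, acceptable with at most 3. Either way the PK patients may have at most 2 DLTs, so

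P(final, as written) = (q³ + 3pq⁵) × P(X ≤ 2 | 6, p).

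At p = 40%: 0.3093 × 0.5443 = 0.168.

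Now let the first three PK patients fill the places up to six, keeping nine in all after 0/3. Only one path changes: no DLT in the first three, two in PK patients 1-3, none in PK patients 4-6. Its probability is 3p²q⁷: 0.0195 at 1/3, 0.0134 at 40% and 0.0059 at 50%.

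| True DLT rate | Final, as written | Final, six first | Difference |
|---|---|---|---|
| 1/3 | 29.1% | 27.2% | 2.0 points (1.95 before rounding) |
| 40% | 16.8% | 15.5% | 1.3 points |
| 50% | 5.9% | 5.3% | 0.6 points |

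**The case against.** Escalating on three clean patients is the declared rolling six rule, and asking for more at the top level is partly a design preference. The footnote that mentions six covers a different case, a level below one already found too toxic, and it counts patients entered, not evaluable. A six-patient rule is no strong guarantee either: 1/6 passes it, with a one-sided 95% upper bound of 58%. All of this stands. The point is about using the three-patient row as a final declaration, not about escalating on it.

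The three-patient stop is also far from certain. Section 3.9 lets therapy start up to five days after enrolment, so the third patient's data may take 28 + 5 = 33 days, longer than the average gap between patients. Section 2.6 reports that Dose Levels 1-3 each enrolled six patients with no DLT. This too stands, and it is why the accrual-weighted figures are given. But no rule ensures that six will be reached.

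A reader might infer that the evidence for the primary result is halved. The documents do not support that. Section 11.1 budgets six further PK patients. Section 2.6 moves the PK cohort to Dose Level 3 only if Dose Level 4 proves intolerable, which implies that it is otherwise run at Dose Level 4. Section 11.2.2 pools those DLTs.

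A reader might also infer that the pooled check lapses, leaving acceptance at 31% for a 40% DLT rate, while infants still gain access to the dose. These cannot both hold, since both rules use the term MTD. If it includes a dose reached under the footnote, the pooled check applies; if not, the infant rule is not triggered either. The definition in 11.2.2 does not require a higher level to have failed, so the first reading is the more natural one.

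Finally, comparing 16.8% with 14.0% at a 40% DLT rate would overstate the benefit. The 14.0% belongs to six plus six patients, not to a design in which PK patients fill the places up to six.

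**Conclusion.** The point holds as a low-cost improvement to the declaration rule. As written, Dose Level 4 can become the recommended dose on three, four or five DLT-free patients. At the declaration this adds at most about 8 percentage points to the chance of accepting a dose with a true DLT rate of 1/3 to 50%, and about 3 to 4 points under the accrual model. Once the PK cohort is pooled, the proposed change is worth about 0.6 to 2 points even with the timing most favourable to an early stop. The main benefit is therefore a firmer basis for the declaration, not a very different final answer.

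These figures rest on assumed DLT rates, on the stated timing or Poisson accrual, and on the PK cohort being run at Dose Level 4 with the pooled rule applied. The last condition is the natural reading, but the plan should state it. It should also say whether the MTD counts as determined before or after the PK cohort is complete, since 5.4.2 depends on that.

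**What to change.** - **Section 11.3, double-asterisk footnote.** Replace with: *At the final dose level, the recommended dose is declared only once six evaluable patients have completed Cycle 1 there with no more than one DLT; until then, if fewer than two DLTs have occurred, the next patient enters at the same level.* Add that the first PK-cohort patients fill the places up to six.
- **Section 11.2.2, third bullet.** Write *at the MTD or recommended dose*, so that the pooled one-third rule plainly covers a dose reached under the footnote.
- **Sections 5.4.2 and 11.1.** Reconcile the term MTD with that wording, so that one meaning applies to both the pooled check and Part A2.

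**Cost.** Three short text changes. The Amendment 5 maximum stays at (6 + 6)/0.8 = 15, and the overall 48 and 56 are unchanged. The declaration may come up to three patients later, about three months at the stated accrual. A tolerable dose is also declared somewhat less often at that point: at a true DLT rate of 20%, 65.5% instead of 70.9% under the step 1 timing.

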11.4 Inclusion of Children, Women and Minorities

The study is open to all participants regardless of gender or ethnicity. Review of accrual to past COG studies of new agents demonstrates the accrual of both genders and all NIH-identified ethnicities to such studies. Efforts will be made to extend the accrual to a representative population, but in a Phase 1 trial which will accrue a limited number of patients, a balance must be struck between patient safety considerations and limitations on the number of individuals exposed to potentially toxic or ineffective treatments on the one hand and the need to explore gender, racial, and ethnic aspects of clinical research on the other. If differences in outcome that correlate to gender, racial, or ethnic identity are noted, accrual may be expanded or additional studies may be performed to investigate those differences more fully.

Racial Categories	DOMESTIC PLANNED ENROLLMENT REPORT				Total	
	Ethnic Categories					
	Not Hispanic or Latino		Hispanic or Latino			
	Female	Male	Female	Male		
American Indian/ Alaska Native	0	0	0	0	0	
Asian	0	3	0	0	3	
Native Hawaiian or Other Pacific Islander	0	0	0	0	0	
Black or African American	6	3	0	0	9	
White	16	19	0	0	35	
More Than One Race	0	3	0	0	3	
Unknown or not reported	0	3	0	3	6	
Total	22	31	0	3	56	

11.5 Pharmacokinetic and Pharmacodynamic Studies and Response Analysis

A descriptive analysis of pharmacokinetic (PK) parameters of pevonedistat will be performed to define systemic exposure, drug clearance, and other pharmacokinetic parameters. The PK parameters will be summarized with simple summary statistics, including means, medians, ranges, and standard deviations (if numbers and distribution permit).

While the primary aim of this study is to evaluate the toxicity of pevonedistat, patients will have disease evaluations performed as indicated in [Section 8.1](#). Disease response will be assessed according to RECIST criteria for patients with solid tumors, and will be reported descriptively.

All these analyses will be descriptive and exploratory and hypotheses generating in nature.

12.0 EVALUATION CRITERIA

12.1 Common Terminology Criteria for Adverse Events (CTCAE)

The descriptions and grading scales found in the revised NCI Common Terminology Criteria for Adverse Events (CTCAE) version 5.0 will be utilized for AE reporting. All appropriate treatment areas should have access to a copy of the CTCAE version 5.0. A copy of the CTCAE version 5.0 can be downloaded from the CTEP web site http://ctep.cancer.gov/protocolDevelopment/electronic_applications/ctc.htm.

12.2 Response Criteria for Patients with Solid Tumors

See the table in [Section 8.0](#) for the schedule of tumor evaluations. In addition to the scheduled scans, a confirmatory scan should be obtained on the next consecutive cycle following initial documentation of objective response.

Response and progression will be evaluated in this study using the revised Response Evaluation Criteria in Solid Tumors (RECIST) guideline (version 1.1).³⁶ Key points are that 5 target lesions are identified and that changes in the *largest* diameter (unidimensional measurement) of the tumor lesions but the *shortest* diameter of malignant lymph nodes are used in the RECIST v 1.1 criteria.

12.2.1 Definitions

12.2.1.1 **Evaluable for objective response:** Eligible patients who receive at least one dose of protocol therapy will be considered evaluable for response. Evaluable patients who demonstrate a complete or partial response confirmed by central review before receiving non-protocol anti-cancer therapy will be considered a responder. All other evaluable patients will be considered non-responders.

12.2.1.2 **Evaluable Non-Target Disease Response:** Eligible patients who have lesions present at baseline that are evaluable but do not meet the definitions of measurable disease and have received at least one dose of protocol therapy will be considered evaluable for non-target disease. The response assessment is based on the presence, absence, or unequivocal progression of the lesions.

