8.2 Radiology Studies

8.2.1 Central Radiology Review for Response: Patients who respond (CR, PR) to therapy or have long term stable disease (SD) (\geq 6 cycles) on protocol therapy will be centrally reviewed. COG Operations Center will notify the Imaging Center of any patient requiring central review. The Imaging Center will then request that the treating institution forward the requested images for central review. The central image evaluation results will be entered into RAVE for review by the COG Operations Center and for data analysis.

The images are to be forwarded electronically to the Imaging Research Center at Children's Hospital Los Angeles via the ImageInBox.

COG institutions that are not connected via the ImageInBox can send the images on CD ROM or USB flash drive. Submitted imaging studies should be clearly marked with the COG patient ID, study number (ADVL1615), and date and shipped to [name] at the address below:

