organ and 5 lesions in total, representative of all involved organs, should be identified as target lesions and recorded and measured at baseline. Target lesions should be selected on the basis of their size (lesions with the longest diameter), be representative of all involved organs, but in addition should be those that lend themselves to reproducible repeated measurements. It may be the case that, on occasion, the largest lesion does not lend itself to reproducible measurement in which circumstance the next largest lesion that can be measured reproducibly should be selected. A sum of the diameters (longest for non-nodal lesions, short axis for nodal lesions) for all target lesions will be calculated and reported as the baseline sum diameters. If lymph nodes are to be included in the sum, then only the short axis is added into the sum. The baseline sum diameters will be used as reference to further characterize any objective tumor regression in the measurable dimension of the disease.

12.2.2.5 **Non-target lesions:** All other lesions (or sites of disease) including any measurable lesions over and above the 5 target lesions should be identified as non-target lesions and should also be recorded at baseline. Measurements of these lesions are not required, but the presence, absence, or in rare cases unequivocal progression of each should be noted throughout follow-up.

12.2.3 **Methods for Evaluation of Measurable Disease**

All measurements should be taken and recorded in metric notation using a ruler or calipers.

The same method of assessment and the same technique should be used to characterize each identified and reported lesion at baseline and during follow-up. Imaging-based evaluation is preferred to evaluation by clinical examination unless the lesion(s) being followed cannot be imaged but are assessable by clinical exam.

12.2.3.1 **Clinical lesions:** Clinical lesions will only be considered measurable when they are superficial (e.g., skin nodules and palpable lymph nodes) and ≥ 10 mm diameter as assessed using calipers (e.g., skin nodules). In the case of skin lesions, documentation by color photography, including a ruler to estimate the size of the lesion, is recommended.

12.2.3.2 **Chest x-ray:** Lesions on chest x-ray are acceptable as measurable lesions when they are clearly defined and surrounded by aerated lung. However, CT is preferable.

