12.2.6 Overall Best Response Assessment

Each patient will be classified according to his “best response” for the purposes of analysis of treatment effect. Best response is determined as outlined in [Section 12.7](#) from a sequence of overall response assessments.

12.3 **Response Criteria for Patients with Solid Tumors and Evaluable Disease****12.3.1 Evaluable Disease**

The presence of at least one lesion, with no lesion that can be accurately measured in at least one dimension. Such lesions may be evaluable by nuclear medicine techniques, immunocytochemistry techniques, tumor markers or other reliable measures.

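### Section 12.2.1.1 counts only centrally confirmed responses, but the central reviews described read images only, so patients with solely non-imaged disease have no route to being counted as responders

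*Combined protocol and SAP*

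**What the plan says.** Three parts of the combined protocol and SAP bear on this.

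- **Responder rule (12.2.1.1).** The denominator is wide: "Eligible patients who receive at least one dose of protocol therapy will be considered evaluable for response". The numerator is narrow: "Evaluable patients who demonstrate a complete or partial response confirmed by central review before receiving non-protocol anti-cancer therapy will be considered a responder". The remainder is assigned by default: "All other evaluable patients will be considered non-responders".
- **Central review (8.2.1 and 12.4.3).** Section 8.2.1 sends patients with CR, PR or long-term stable disease to central radiology review. What goes in is images: "The Imaging Center will then request that the treating institution forward the requested images for central review". What comes out is image results: "The central image evaluation results will be entered into RAVE for review by the COG Operations Center and for data analysis". Section 12.4.3 adds central Curie scoring of MIBG scans.
- **Disease that need not be imaged.** Section 4.1.3 admits measurable or evaluable disease. On evaluable lesions, 12.3.1 says: "Such lesions may be evaluable by nuclear medicine techniques, immunocytochemistry techniques, tumor markers or other reliable measures". Section 12.3.2 defines CR for such disease. Section 12.5.1 defines marrow CR by morphology. Section 12.2.3.1 allows lesions measured by calipers: "Clinical lesions will only be considered measurable when they are superficial".

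**The concern.** The responder rule depends on a confirmation step that, as described, cannot be carried out for some patients whom the protocol enrols and for whom it writes response criteria. This is more than a gap in the text, because the default clause turns the absence of central confirmation into a recorded non-response.

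At stake is the response summary for aim 1.2.1 (preliminary antitumor activity). Part of the denominator may be failure by construction, and two classifications in the same protocol may disagree about one patient with nothing to say which is reported. Section 11.5 says only that response will be described using RECIST; it does not choose between 12.2.1.1 and 12.7. DLT assessment, the MTD and the sample size do not depend on this.

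**Working it through.** The plan states no response rate, target or decision rule, so there is no figure to reproduce. The check is mainly textual.

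**Step 1. Which central reviews of response are described?** Two: 8.2.1 (radiology) and 12.4.3 (MIBG/Curie). Section 14.1 mentions biopathology reviews, but only as a category of research record, with no response-review procedure attached. No section routes marrow slides, cytology or physical findings to central confirmation of response. That central review means images only is therefore an inference from the procedures described; 12.2.1.1 itself just says central review.

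**Step 2. Which non-imaged disease has a response criterion?**

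- *Marrow only (neuroblastoma).* Section 12.5.1 gives CR on two consecutive clear bilateral samples at least 21 days apart, with markers normalised if raised at enrolment. Section 4.1.7.1.b admits known marrow disease, and 8.1 schedules repeat marrow evaluation.
- *Evaluable disease by immunocytochemistry.* Section 12.3.2 gives CR when it has all disappeared; 12.3.3 rules out PR.
- *Caliper-measured superficial lesions.* Sections 12.2.2.1 and 12.2.3.1 make them measurable at 10 mm or more, so the CR and PR rules of 12.2.4 apply. Section 12.2.3 prefers imaging but provides for lesions that can only be examined clinically.
- *Tumor markers alone.* Section 12.2.3.5 bars response on markers alone, while 12.3.1 lists markers among the means of evaluating disease. Those two sections conflict with each other, so markers are left out of this point.
- *CSF cytology alone (CNS).* Section 12.6.2 lists it as evaluable, but the only CR row in the 12.6.7 table requires target lesions in CR. It is not shown that such a patient can meet a protocol CR.

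**Step 3. What happens to a patient in the first three groups with no imageable disease?** Under 12.2.1.1 there is no described route to confirmation, so the patient is a non-responder. Under Table 6 in 12.7, CR at two consecutive assessments gives a best response of CR, with no mention of central review. Sections 12.2.6, 12.3.6 and 12.5.2 all point to 12.7 for the analysis of treatment effect.

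**Step 4. How large is the effect of one such patient?** Change in rate = 1/n, with n from 11.1:

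- n = 12 (Dose Level 4, 6 + 6 for PK): 1/12 = 8.3 points; for example 2/12 = 16.7% reported instead of 3/12 = 25%.
- n = 18 (enrolled in Part A1 as of 6/30/19): 1/18 = 5.6 points.
- n = 56 (absolute maximum): 1/56 = 1.8 points.

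**Step 5. How large is the expected effect?** Let f be the share of patients with only non-imaged disease. The documents give no f, so this is an assumption. If the true rate is the same in both groups, reported rate = (1 − f) × true rate. For an assumed true rate of 10%:

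- f = 5%: 0.95 × 10% = 9.5%
- f = 10%: 0.90 × 10% = 9.0%
- f = 20%: 0.80 × 10% = 8.0%

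The equal-rate assumption may overstate the loss, since 12.3.3 allows no PR in evaluable-only disease.

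**The case against.** The strongest reply has four parts.

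**Central confirmation is a deliberate, conservative choice**, openly stated, and a strict responder count can sit beside a best-response classification without contradiction. That is a fair defence where a response can be reviewed and is not upheld. It does not cover a response that no described review can examine.

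**Scope.** Section 12.2.1.1 sits under 12.2, while 12.3, 12.5 and 12.6 carry their own criteria, and 12.2.1.2 defines evaluability for non-target disease without mentioning central review. This stands in part: the protocol does not say that 12.2.1.1 governs those sections. But if it does not, they have no responder definition at all, since 12.2.1.2 does not supply one. Caliper-only patients fall inside 12.2 on either reading.

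**The affected groups are narrow.** Tables 4 and 5 treat marrow as one column beside imaging, and no table gives an overall response for marrow alone, so a marrow-only CR under 12.7 rests on a step that is not tabulated. The central MIBG category of CR in 12.4.3 includes a marrow condition, but only for MIBG-positive patients. Photography of skin lesions is recommended in 12.2.3.1, but 8.2.1 does not send photographs for review. The narrowness stands, and it limits the size of the point.

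**The aim is secondary and descriptive** (1.2.1, 11.5), and the number of such patients is unknown. This also stands.

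A reader might go further and infer that anyone followed by marrow, cytology, tumor markers or examination can never be a responder. The documents do not support that. Patients who also have CT/MRI or MIBG disease can be confirmed on their images; a marker-only non-response agrees with 12.2.3.5; and a cytology-only CR has no row in the CNS table.

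**Conclusion.** The point holds for patients whose disease is assessable only by marrow morphology, immunocytochemistry, or calipers on superficial lesions that cannot be imaged. The stated rule scores them as non-responders whatever their course, while 12.7 can record a CR for the same patient.

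Its reach is the secondary activity summary. Each such response is worth 8.3 points in 12 patients, 5.6 in 18 and 1.8 in 56, and the number may be zero. The conclusion rests on two readings: that central review means the two imaging reviews described, and that 12.2.1.1 is meant to apply across Section 12. If either is wrong, the text should say so, and the edit below would still be useful.

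**What to change.** Amend 12.2.1.1 to state that:

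1. central-review confirmation applies to responses assessed by imaging, including MIBG;
2. where disease is assessable only by marrow morphology, immunocytochemistry or clinical examination, a response that meets the Section 12 criteria and confirmation rules on institutional assessment counts as a response, and is tabulated separately from centrally confirmed responses;
3. this definition governs 12.3, 12.5 and 12.6.

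Leave tumor markers out of that sentence and reconcile 12.2.3.5 with 12.3.1. State how CNS disease evaluable only by CSF cytology maps to the 12.6.7 table.

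The cost is a short text amendment with no new reviewer, sample or procedure. The downside is that a few responses would rest on institutional assessment. Separate tabulation labels them as such, and anyone who wants the strict count can still read it directly.
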